Aim 1 & 2 assessment data will be collected from 600 Veteran/partner dyads (up to 200 per site, 100 dyads per arm) via a secure project website at baseline, 1, 2, and 4 months to assess primary and secondary outcomes. MR utilization and pain ratings will be assessed weekly for the first eight weeks of the intervention. This data collection plan will allow assessment of acute changes, rate of change with repeated measures over two months and sustained changes.

In **Aim 3**, a sub-sample of 84 individuals assigned to the intervention arm (n= 84 individuals, approximately 28 individuals/site) will be purposively selected (e.g., high or low MR utilization groups) to participate in telephone interviews to evaluate their experiences using the program. All consenting participants will be randomly assigned in a 1:1 ratio *using a permuted variable block design* to one of two arms (treatment vs. control). Participants will receive study information, instructions on how to complete the online data collection, and contact information in case they experience an adverse event. Participants will provide preferred contact information for data collection reminders. We will have contact information for each participant's primary care provider to ensure contact in the case of an adverse event and follow our established protocol for such events.

Treatment Arm: MR is a user-driven, dyadic, self-care management program developed with NIMH funding (R43/44) for use by Veterans and their selected partners, individually or together, to reduce pain and distress and support physical, mental, and relationship health. MR was designed for Veterans who face obstacles accessing formal mental health services. It can also be used to complement formal services. MR is a patient-centered intervention, allowing users to determine the pace at which to proceed in each program component.

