Exclusion criteria will be: Moderate to severe TBI, diagnosis or documented treatment for psychosis in previous 6 months, currently in high-intensity substance use disorder treatment, non-English speaking; visual, hearing, cognitive impairment that prevent participation or ability to consent, self-report history of partner/family member physical abuse in the past year, and/or lack of access to internet service. These individuals will be excluded due to medical, language, and technology access issues that would prevent safe and full study participation. As stated above, *potential participants who screen for aggression or violence will also be excluded from study.*

Randomization: Participants (dyads) will be randomized to treatment (MR) or control using a per site variable block randomization method (blocks of 6 and 8) to facilitate a balance in treatment and control group sizes per site and over time. Variable blocks of 6 and 8 per site will be randomly used so that no one will know for sure the next random assignment. Dyad is the unit of randomization; this ensures that members of the same couple receive the same intervention. The randomization will be stratified by whether or not the veteran is currently receiving, or has received in the past 2 weeks, a Level 1 evidence-based treatment for pain and/or PTSD, per current VA-DoD treatment guidelines.

This will facilitate subgroup analyses of the effect of the MR intervention in the presence versus absence of concomitant first-line evidence-based treatment for pain and PTSD. A computer-generated random allocation sequence will be generated by the study biostatistician (separately for each site/era of service combination to ensure balance across sites, that is, control for site effects by design). [name] and [name] will be responsible for monitoring participant (dyad) assignment. Participant dyads randomized to the treatment group will receive a link, and PIN to access the MR site and will be instructed to create personal user accounts. Control group members will receive access to MR after completing data collection.

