A) Recruitment and Informed Consent and HIPAA Authorization:

Prior to recruitment, we will obtain IRB and VA R&D Scientific Review Committee approval to conduct this proposed research.

Recruitment. We will obtain a HIPAA authorization waiver for recruitment purposes. Identified patients will be sent a letter via mail or from their provider on behalf of the PI explaining the study and asking if patients would be willing to participate in the study. Veteran will contact the study team member by telephone and at that time team member can gauge Veterans willingness and appropriateness to participate. This recruitment method has been successfully used in previous studies conducted by this team and other R&DS projects. Recognizing the potential limitation of this strategy given the inclusion/exclusion criteria we will also gain IRB approval to collaborate with the Tampa R&DS Veteran Engagement Council and co-investigators to recruit Veteran participants using other recruitment means such as referrals and advertisements (e.g. poster, brochures, flyers). As described under Sampling on page 23 of these potential participants who contact study staff or who are contacted by study staff will be presented with information about the study to help them determine whether they'd like to participate in the study and give verbal consent and HIPPA authorization. If we do not get an adequate recruitment response, we will implement the snowball recruitment technique that involves asking participants to inform and encourage friends, colleagues, and other peers to participate.

Informed Consent. A waiver of informed consent process for recruitment purposes (medical record review), and a waiver of consent for a Verbal Consent Document for

participant phone screening will occur. Please note, the study team will also be utilizing a Written Consent Document or verbal consent via telephone. Participants will have an option to complete the informed consent and HIPAA authorization for study, in person or over-the-telephone. During recruitment contact and calls, research team members will review the consent and HIPAA content with participants, to ensure review and comprehension. Since both partners will be full and equal participants in the study, both will be individually screened and consented by individual interview.

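### The published block sizes of 6 and 8 do not give the stated guarantee that no assignment can be known in advance, and the plan states no other concealment safeguard

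*Combined protocol and SAP*

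**What the plan says.** The Randomization paragraph of the protocol specifies variable blocks of 6 and 8 within site and draws this conclusion: "Variable blocks of 6 and 8 per site will be randomly used so that no one will know for sure the next random assignment". Study Design and Overview gives the ratio: "All consenting participants will be randomly assigned in a 1:1 ratio". The dyad is the randomised unit.

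The strata are described in more than one way. Blocks are per site. Then "The randomization will be stratified by whether or not the veteran is currently receiving" (or received in the past 2 weeks) a Level 1 treatment for pain or PTSD. The sequence is also generated "separately for each site/era of service combination to ensure balance across sites". The number of era levels is not given.

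The study biostatistician generates the sequence, and two team members monitor assignment. The Sampling section discloses assignment when baseline data collection is complete. MR dyads then get a link and PIN, while waitlist dyads get access only after data collection ends. On recruitment, the section on protection from risk says that the Veteran telephones the team and "at that time team member can gauge Veterans willingness and appropriateness to participate".

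The text does not say who is kept from seeing earlier assignments, or whether those who monitor assignment are separate from those who recruit.

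**The concern.** The sentence on variable blocks is the only protection against prediction that the plan offers, and it is worded as a guarantee. Varying the block size works by hiding where a block ends. Once the possible sizes are printed, the largest size caps how often one arm can occur in a block, and some histories then leave only one possible next assignment.

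The conditions under which this could matter are present. The arms are distinguishable after assignment, and the Table 1 weekly utilization forms also differ by arm. Table 3 plans only 3 to 4 dyads per month per site, slow enough for recent assignments to be remembered. Staff have some discretion at first contact. If a recruiter could foresee the next arm, who is enrolled and when could depend on it, and randomisation would no longer protect the comparison from selection.

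**Working it through.** **Inputs.** Block sizes 6 and 8 (Randomization); 1:1 ratio and 600 dyads, up to 200 per site (Study Design and Overview). *Assumptions not in the documents:* the two sizes are equally likely unless stated otherwise, and strata within a site are of equal size. List length is then 200 per site with no further strata, 100 with two strata, and 50 with four. The worst-case observer knows the sizes, every earlier assignment in the list, and which list the next dyad will use.

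**The plan's own figure.** The plan claims, in effect, that 0% of assignments are certain. This is not reproduced.

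**Exact check, start of a list.** A block of 6 holds three of each arm and a block of 8 holds four. Four of one arm within the first six places therefore proves a block of 8, and once the four are used up its remaining places all go to the other arm. A block of 8 has C(8,4) = 70 orderings and is drawn with probability 1/2.

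- Place 5 certain: four alike in the first 4 places, 1/2 × 2 × C(4,4)/70 = 1/70 = 1.4%
- Place 6 certain: four of one arm in the first 5, 1/2 × 2 × C(5,4)/70 = 5/70 = 7.1%
- Place 7 certain: four of one arm in the first 6, 1/2 × 2 × C(6,4)/70 = 15/70 = 21.4%
- Place 8 certain: the same histories, 21.4%. A 3:3 split at place 6 proves nothing, because a new block may have started.

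Places 1 to 4 are never certain.

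**Whole lists.** Later in a list the block boundaries are less clear, so the share falls. Simulation with Bayesian updating over block size and position gives:

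| Dyads in list | Certain | Lists with at least one | Guessed correctly |
|---|---|---|---|
| 50 | 4.2% | 55% | 66.9% |
| 100 | 3.8% | 75% | 67.1% |
| 200 | 3.8% | 93% | 67.2% |

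Over 600 dyads: 600 × 0.038 = 23 to 600 × 0.042 = 25 certain assignments.

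**Size mix.** At 50 per list, using sizes 6 and 8 in a 75:25 mix gives about 2.0% certain, and 25:75 gives up to 6.5% across repeated runs. That is 600 × 0.020 = 12 to 600 × 0.065 = 39.

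**Where the 67% comes from.** For a known block of size 2m, the expected number of correct guesses is m + 2^(2m−1)/C(2m,m) − 1/2.

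- m = 3: 3 + 32/20 − 0.5 = 4.10, and 4.10/6 = 68.3%
- m = 4: 4 + 128/70 − 0.5 = 5.33, and 5.33/8 = 66.6%
- Together: (4.10 + 5.33)/14 = 67.3%

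Always naming the arm that is behind needs no knowledge of the sizes, and in simulation it scores the same as the optimal rule (66.9% at 50 per list). The guess rate is a feature of 1:1 blocking with visible history.

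**Weaker observers (200 dyads per site).** With past assignments tracked by stratum but the next dyad's stratum unknown, under 0.1% are certain with two strata per site and none were seen with four or six. Correct guesses are 63%, 59% and 57%. If all strata are pooled and the arm behind is named, correct guesses are 61.9%, 58.3% and 56.7%.

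**The case against.** The strongest objection is that the observer is assumed. Nothing says that recruiters see running assignments or know which list the next dyad will use. Concurrent treatments are recorded in the baseline survey, the discretion quoted above is exercised on the first telephone call, and assignment is disclosed only after baseline. At that call the stratum may well be unknown, and then certainty all but disappears. This stands, and it is why the 4% is a worst case. It does not rescue the sentence, which is worded for everyone and without conditions.

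A reader might infer that printing the sizes is what makes two in three assignments guessable. It is not: the same rate is reached without knowing them. Only the certain assignments depend on disclosure.

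A reader might also take about 25 of 600 as the number of assignments that staff would actually know, or conclude that enrolment was biased. The documents support neither. Staff access to the history is not described, no effect on the pain outcome has been estimated, the Veteran initiates contact, and listed eligibility criteria limit staff discretion.

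Finally, role separation may exist in practice. The biostatistician generates the list, nothing says that person recruits, names are removed and the study-flow figure is not shown.

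**Conclusion.** The stated property does not hold. For an observer who knows the sizes, the history and the stratum, about 4% of assignments are certain when the sizes are used equally often, and about 2% to 6.5% over the mixes tried. The share is near zero if the next stratum is unknown. The guess rate of about 67% against 50% by chance (57% to 63% without separable strata) is a separate matter, governed by who can see past assignments rather than by whether the sizes are published. The trial is not described as open-label; that the arms are evident is inferred from the immediate versus delayed access. The practical weight is modest: an over-strong claim and an unstated concealment procedure, which leave an opportunity for selection bias without showing that any occurred.

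**What to change.** 1. Remove the block sizes from the protocol and all staff documents and hold them in a restricted randomisation file.
2. Replace the sentence with: *block sizes are varied and not disclosed to study staff*.
3. State that the list is held, and running assignments by stratum are kept, away from anyone who screens or consents. This step addresses the guess rate; the first two address only certainty. It also requires the Randomization paragraph to settle which strata define a list.
4. If dyads remain to be randomised, draw from a wider undisclosed set of sizes. Even if disclosed, a set of 4, 6, 8, 10 and 12 gives 0.7% certain and 65.7% guessed at 50 per list, so the gain is mainly in certainty.
5. If enrolment is complete, drop the claim and report how allocation was concealed. The updated SAP describes interview coding in the past tense, so a regenerated list may be moot.

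The cost is mostly wording. Step 4 also needs a new list and allows a slightly larger imbalance within a stratum.

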Sample Size Power Analysis: Aim 1&2, H1.1-H1.2 & H2.1 estimates of statistical power are based on Aim 1 and initially the primary outcome of pain. Whereas dyad is the unit of randomization, we assess power based on separate analyses for Veterans and partners (one approach used). There are 4 major intervals of assessment (baseline, 1, 2, and 4-months). At the beginning of this study, we estimated attrition based off of a previous MR trial that had less than 5% attrition. Based on early recruitment at the primary site, we have adjusted recruitment goals to allow for approximately 33% attrition, and uneven recruitment across the three study sites. Assuming within-subject (outcome measurement) correlation of 0.5, the proposed sample size will provide 80% power (2-sided type I error rate of 0.05) to detect a “small-to-medium” effect size of 0.38 (Cohen’s d). For analyses stratified by site (in addition to evaluation by random effect assessment), the study will provide 80% power to detect a “medium-to-large” effect size of 0.66. By way of comparison, the pilot data presented above describes large effect sizes ($d = 0.81$ for pain symptom reduction). While this effect size was based on a relatively small sample of comparable patients ($n < 15$) and within-subject assessment (paired t -test), it provides good assurance that the proposed sample size is sufficient to detect realistic, medium size effects should they exist with the MR program. For secondary outcomes, we will use a type I error rate of 0.01 for multiple comparisons. For the sample and our described assumptions, this will provide 80% power to detect a “medium” effect size of 0.45.⁵⁹

Sample Size: Qualitative- Aim 3 sample size relies on the quality and richness of information obtained.⁶⁰ Conceptual saturation is the goal of qualitative research, and depends on data to support interpretations. Saturation has been noted to occur within the first 12 interviews.^{60,61} Our team has extensive experience in evaluating electronic technologies, and have found recruiting high and low volume users provides the richest dataset. To ensure representative data, we will conduct telephone interviews with a purposive (e.g., high or low MR utilization group) sub-sample of up to 84 individuals to achieve representation at each site (approximately 28 individuals/site).

Data Collection Procedures. Data will be collected using (1) self-report surveys; and (2) telephone interviews.

(1) Self-reported Survey Data.

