Interviewers will solicit respondents' attitudes, opinions, and reports about their preferences and the pros and cons of MR and/or participating in the practice groups, including their perceptions of usefulness. We will use standard communication techniques to stimulate discussion, with prompts (e.g., "tell me more"), summarizing statements, and silence. We have used these methods in several previous studies to gather data effectively. Additionally, in an effort to understand the factors that contribute to study attrition, a maximum of ten individuals who did not complete study activities may be contacted for a brief 15-minute voluntary telephone interview. These interviews will solicit respondents' experiences with the study and any difficulties that they experienced. Only participants who were lost to follow up and who had been assigned to the treatment arm will be contacted for these attrition interviews. Participants who officially withdrew from the study will be excluded from the pool of prospective interviews.

A total of 84 interviews (n=84 individuals), including participants lost to follow up and participants who have successfully completed the study, will be performed. We will attempt to interview both members of dyads to obtain conceptual saturation.

Data Analysis: The *intention to treat* principle will be used for all analyses irrespective of the extent of protocol compliance or dropout.⁹⁰ Whereas randomization is anticipated to balance both study arms on presenting demographic and clinical characteristics, including

within sites and by concomitant receipt of first line pain and/or PTSD treatment, continuous variables will be compared by student t-tests or Wilcoxon tests (depending on distributional properties); categorical variables will be compared by chi-square analyses.

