Hypotheses Aims 1 & 2. All outcome measures (*primary and secondary*) under Aim 1 will be collected at baseline, 1, 2, and 4 months and are continuous variables. Therefore, general linear mixed models will be used with main effects terms for GROUP (MR vs. waitlist) and TIME (4-time points) and a GROUP x TIME interaction term (for rate of change). The models will also include site as a random effect. To assess whether the rate of change is curvilinear (i.e., the rate of change differs between time points), a quadratic parameter will be tested. Different correlation structures and functional forms of the effects of the MR program will be assessed using the information criteria and a final parsimonious model will be determined for final statistical inference. Initial effects of the MR program (baseline to 1-month) will be evaluated by analysis of covariance (ANCOVA). For H1.1, the primary outcome measure for pain will be total score on the 19-item POQ. For H1.2., the primary outcome measure for PTSD will be total score on the 20-item PCL-5. Subgroup analyses will be explored using similar methods and examination of severity of baseline pain and PTSD scores. These analyses will provide insight into subgroups in whom the MR program may be particularly beneficial. In a similar realm, analyses will be stratified by baseline median level of relationship satisfaction, as derived from total score on the 14-item RDAS. This will permit assessment of the effect of the MR intervention on potential improvement in relationship satisfaction among a cohort of dyads with presumably troubled relationships at entry. Moreover, using the weekly reports (8 weeks) of MR use and satisfaction with the MR program, the MR sample will be split above versus below the median for these two measures, and compared separately against the waitlist control condition at 2-months. This approach approximates a “per protocol” analysis in terms of recommended use of the MR program. In addition, especially for Aim 2 outcomes, we seek to examine whether dyads appear to show mutual benefits from the MR program. Therefore, multilevel models will be fit using an over-time dyadic model⁷⁸ in which individuals are nested within dyads and time is crossed with dyads (i.e., both Veteran and partner are assessed at the 4 time points). This analysis accounts for the non-independence due to the correlation between dyad members’ general levels on outcomes averaged over time, as well as the time-specific correlation between their outcomes (e.g., similarity caused by time-specific events).

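### Level 1 treatment and era of service are named as randomisation factors, but neither enters the Aim 1–2 models; the cost is a slightly conservative test and a little lost precision

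*Combined protocol and SAP*

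**What the plan says.** The Randomization section describes the allocation in three statements. Dyads are allocated "using a per site variable block randomization method (blocks of 6 and 8". Then: "The randomization will be stratified by whether or not the veteran is currently receiving, or has received in the past 2 weeks" a Level 1 treatment for pain and/or PTSD. Finally, the biostatistician generates the sequence "separately for each site/era of service combination to ensure balance across sites". Site and era are therefore expressly paired. How Level 1 joins them is not stated, and the era levels are not defined. The section gives a purpose for the Level 1 stratum: "This will facilitate subgroup analyses of the effect of the MR intervention in the presence versus absence of concomitant first-line evidence-based treatment".

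The Data Analysis section expects balance "within sites and by concomitant receipt of first line pain and/or PTSD treatment". Era is not mentioned there.

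Under Hypotheses Aims 1 & 2, the model has group, time and group by time, with a quadratic time term to be tested. It adds: "The models will also include site as a random effect". The Updated Statistical Analysis Plan lists group, continuous time and group by time, and refers to the protocol's Table 1 for the measures. Neither model has a Level 1 or era term.

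Two related statements do not fill the gap. The Conceptual Framework speaks of controlling for treatment history, and Table 1 labels self-reported concurrent treatment a covariate. Neither is carried into a stated model. The Table 1 item is collected at baseline and again at months 1, 2 and 4, after randomisation.

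**The concern.** Blocked allocation within strata makes the arms more alike on the stratifying factors than chance alone would. If those factors predict the outcome and the model ignores them, the standard error is computed as if that balance had not been arranged. It comes out too large, so p-values are slightly too high and some precision is lost. Including factors already used to randomise recovers this at almost no cost.

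Here the analyst cannot do so from the text, because the text does not settle which lists were used. Level 1 status is also clinically central. The Study Design section presents the programme as an adjunct to conventional evidence-based treatment, and receipt of such treatment could plausibly be related to change in pain.

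**Working it through.** **The plan's own figure.** The Sample Size Power Analysis gives d = 0.38 at 80% power, two-sided alpha 0.05.

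- Per-arm number: 2 × (1.96 + 0.8416)² / 0.38² = 108.7, so 109 per arm (218 analysed).
- Per-site check: 2.8016 × √(2 / (109/3)) = 0.657, which matches the stated 0.66. The two figures agree with each other.
- They do not follow from the planned 600 dyads. The same section says "we have adjusted recruitment goals to allow for approximately 33% attrition". Then 600 × 0.67 = 402, or 201 per arm, with 96.8% power at d = 0.38. That mismatch is a separate matter, so both sizes are carried below.

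**Inputs.** From the documents: 1:1 allocation, d = 0.38, alpha 0.05, retention r = 0.67. Assumed, because the documents give no value: loss is random, and Level 1 explains R² = 2, 5 or 10% of the variance of the analysed contrast (change, not level).

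**Formulas.** Blocks balance the dyads as randomised, and random loss leaves part of that balance. With SD = 1 and n analysed per arm:

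- True variance of the unadjusted difference: (2/n)(1 − r·R²). The unadjusted model uses 2/n.
- Actual alpha: 2 × [1 − Φ(1.96 / √(1 − r·R²))].
- With c = 0.38 / √(2/n), unadjusted power is Φ((c − 1.96) / √(1 − r·R²)) and adjusted power is Φ(c / √(1 − R²) − 1.96).
- c = 3.810 at n = 201 and 2.805 at n = 109.

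**Results if Level 1 was a stratum and is omitted.**

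| R² | Actual alpha | Power, 201 per arm: unadjusted / adjusted | Loss (points) | Power, 109 per arm: unadjusted / adjusted | Loss (points) |
|---|---|---|---|---|---|
| 2% | 4.8% | 96.87 / 97.05 | 0.2 | 80.26 / 80.89 | 0.6 |
| 5% | 4.6% | 97.00 / 97.43 | 0.4 | 80.51 / 82.07 | 1.6 |
| 10% | 4.2% | 97.22 / 98.01 | 0.8 | 80.93 / 84.06 | 3.1 |

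Without attrition (r = 1) the alphas would be 4.8, 4.4 and 3.9%.

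**Simulation check.** 8,000 runs used site by Level 1 strata, blocks of 6 and 8, 33% random loss, and assumed site shares of 50/30/20% and Level 1 prevalence of 30%. With 600 randomised, alpha was 4.7/4.5/4.2% and power 96.9/97.0/97.3% unadjusted against 97.1/97.4/98.0% adjusted. This agrees with the formulas within simulation error.

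**How large must the Level 1 effect be?** At 30% prevalence, R² = 0.3 × 0.7 × δ², so 2, 5 and 10% need a difference in change between Level 1 and other Veterans of 0.31, 0.49 and 0.69 SD. The 10% row needs almost twice the planned treatment effect and is an upper case.

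**The announced subgroup.** The standard error of a group by Level 1 interaction is √(2 / (n·p(1 − p))). For an interaction of 0.38 SD and assumed prevalence p of 20% to 50%, power is 33% to 48% at 201 per arm and 20% to 29% at 109.

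**The case against.** The strongest reply is that this is a small documentation matter, and most of that stands.

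- *A reader might infer that the three randomisation statements cannot be put together.* The text does not support that. Site and era are explicitly paired, blocks are per site, and the Data Analysis section expects balance by site and first-line treatment. Reading the factors as cumulative is natural. Only the place of Level 1, and the era levels, remain open.
- *A reader might infer that the updated SAP drops site.* It does not say that it replaces the protocol model, it refers back to the protocol, and the random site effect is never withdrawn. The power section also plans for site: "For analyses stratified by site (in addition to evaluation by random effect assessment". A site main effect largely cancels from group by time in any case.
- *A reader might infer that the Level 1 subgroup is wholly unspecified.* The Randomization section gives the contrast in words, and the Aims 1 & 2 text says subgroups are explored by similar methods, after defining the mixed model and the POQ total as the H1.1 outcome. What is missing is confirmation that this covers Level 1. Its low power is not a defect in an exploratory analysis for which no power is claimed.

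It can also be said that concurrent treatment is already a covariate. It appears in no stated model, and its later values could be affected by the intervention, so it does not stand in for the stratum.

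What survives is that factors named as strata are missing from both models.

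**Conclusion.** The point holds at minor severity. Level 1 status and era are named in the randomisation but not in either Aim 1–2 model. If they were strata and predict change, the test is slightly conservative: on the assumed R² of 2 to 10%, alpha is about 4.8 to 4.2%, and power falls by 0.2 to 0.8 points at 201 per arm or 0.6 to 3.1 at 109.

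It would be wrong to infer a raised false-positive risk, since the error runs the other way. No primary conclusion turns on this alone. The sizes rest on assumed R² and random loss; the documents do not give R², Level 1 prevalence or the number of era levels. If the records show that Level 1 was not a stratum, the alpha argument for it falls away, and adjustment is then only an ordinary gain in precision.

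**What to change.** 1. Confirm from the allocation records which strata were used, and correct the Randomization section to match.
2. Add those strata to the Aim 1–2 models as dyad-level baseline terms **with their interaction with time**. A main effect alone largely cancels from group by time.
3. Use the Level 1 value recorded at randomisation. If Level 1 was not a stratum, or was not recorded then, use only the baseline concurrent-treatment item, never the month 1, 2 or 4 values.
4. Minor wording: state in the updated SAP that the protocol's site term is kept. Confirm that the announced Level 1 subgroup is one exploratory group by time by Level 1 contrast on the POQ total, reported with its confidence interval.
5. The updated SAP reports the qualitative analysis in the past tense. If outcome data have been seen, label any added term, any added contrast, **or any withdrawal of the announced subgroup** as a late change.

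The cost is a records check, some SAP wording and a few degrees of freedom. No new participants or data collection are needed.
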